9.5. Grading of Severity of Adverse Events

The severity of AEs will be graded using CTCAE v 4.0 (refer to the study manual). For each episode, the highest severity grade attained should be reported.

If a CTCAE criterion does not exist, the Investigator should use the grade or adjectives: Grade 1 (mild), Grade 2 (moderate), Grade 3 (severe), Grade 4 (life-threatening), or Grade 5 (fatal) to describe the maximum intensity of the AE. For purposes of consistency with the CTCAE, these intensity grades are defined in [Table 4](#).

Table 4: Grading of Adverse Event Severity

Grade	Adjective	Description
Grade 1	Mild	Sign or symptom is present, but it is easily tolerated, is not expected to have a clinically significant effect on the patient's overall health and well-being, does not interfere with the subject's usual function, and is not likely to require medical attention
Grade 2	Moderate	Sign or symptom causes interference with usual activity or affects clinical status, and may require medical intervention
Grade 3	Severe	Sign or symptom is incapacitating or significantly affects clinical status and likely requires medical intervention and/or close follow up
Grade 4	Life-threatening	Sign or symptom results in a potential threat to life
Grade 5	Fatal	Sign or symptom results in death

Note the distinction between the seriousness and the severity of an AE. Severity is a measure of intensity; thus, a severe reaction is not necessarily a serious reaction. For example, a headache may be severe in intensity but would not be classified as serious unless it met one of the criteria for serious events listed in [Section 9.1.2](#).

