6.2.2. Duration of Treatment

The study duration will be 4 weeks during the PK portion and 48 weeks during the extension period (52 weeks total). Initial data assessment and reporting will be after all patients complete first 4 weeks (safety and PK) to satisfy Pediatric Investigation Plan (PIP) requirements and an additional report will be issued after completion of 48 weeks extension). The study may be terminated by the sponsor at any time and for any reason, eg, the clinical development of ataluren in dystrophinopathy is discontinued.

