9.3. Adverse Event Recording

All AEs (both serious and non-serious) that occur in patients during the AE reporting period must be recorded, whether or not the event is considered drug related. In addition, any known untoward event that occurs subsequent to the AE reporting period that the Investigator assesses as possibly related to the investigational drug/product should also be recorded as an AE.

All AEs are to be recorded in the source documents and on the eCRF using concise medical terminology; whenever possible terms contained in Medical Dictionary for Regulatory Activities (MedDRA) should be employed. In addition, the following information should be recorded:

- Indication of whether the event is serious or non-serious (see [Section 9.1.2](#))
- Relationship to study drug (see [Section 9.4](#))
- Severity of the event (see [Section 9.5](#))
- Onset date
- Resolution date, or date of death
- Action taken
- Outcome of the event

Classification of the event as serious or non-serious determines the reporting procedures to be followed.

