11.3. General Statistical Considerations

By-subject listings will be created for each eCRF module. Summary tables for continuous variables will contain the following statistics: N, mean, median, standard deviation, standard error, minimum, maximum, and 95% confidence intervals (CIs) as appropriate. Summary tables for categorical variables will include N and percentage. Graphical techniques will be used when such methods are appropriate and informative.

Transformations of the data may be explored if warranted by the distribution of the data.

All analyses will be performed using Statistical Analysis System (SAS® Version 9.0 or higher).

The primary analysis will be conducted on data obtained during the 4-week PK period of the study and may be reported separately from the extension study data.

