12.1.3.2 Summary of adverse events by System Organ Class and Preferred Term

Table 14.3.1.2.1 entitled *Summary of Treatment-Emergent Adverse Events by System Organ Class and Preferred Term (Safety Population)* contains the primary presentation of the AE data. This table is prepared without regard to causality or relationship to the study drug. Subjects will be counted only once at the SOC level and will be counted once for each applicable PT; multiple occurrences of the same PT for a subject will be counted only once. The number and percentage of subjects experiencing each SOC and PT will be displayed. SOCs, and PTs within SOC, will be displayed alphabetically. The overall incidence of AEs will be summarized using counts and percentages by phase of study.

Table 14.3.1.2.2 entitled *Summary of Adverse Events that Occurred in the 4-Week Follow-up Phase by System Organ Class and Preferred Term (Safety Population)* contains a summary of only those adverse events which occurred within 4 weeks after the last dose of study medication. The number and percentage of subjects experiencing adverse events for each body system and preferred term will be displayed by phase of study.

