12.1.3.3 Assessment of Severity

All adverse events, both serious and non-serious, will be assessed for severity or intensity. The investigator or designee will use the following classification to rate the severity of each AE. Section 9.5 of the protocol contains the description of each of these severity grades.

- CTCAE Grade 1 Mild
- CTCAE Grade 2 Moderate
- CTCAE Grade 3 Severe
- CTCAE Grade 4 Life-threatening
- CTCAE Grade 5 Fatal

Table 14.3.1.3 entitled *Summary of Treatment-Emergent Adverse Events by System Organ Class, Preferred Term and Severity (Safety Population)* provides the presentation of adverse events with respect to the severity or intensity of the event using the scale presented above. Subjects with multiple occurrences of the same system organ class or preferred term will be summarized at the maximum severity reported for that AE. The number and percentage of subjects experiencing adverse events for each body system and preferred term will be displayed by phase of study.

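### With one onset date and one highest grade per adverse event, and no phase-assignment rule, the severity-by-phase table can place later worsening in the 4-week PK phase

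*Protocol*

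**What the plan says.** **Recording.** Protocol 9.3 lists the items to record for each AE. They include "Severity of the event" (with a pointer to 9.5), one onset date and one resolution date. No date of a grade change is listed. Protocol 9.5 then fixes which grade is kept: "For each episode, the highest severity grade attained should be reported". The term episode is not defined.

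**Tabulation.** SAP 12.1.3.3 (Table 14.3.1.3) says that subjects with repeated events "will be summarized at the maximum severity reported for that AE", and continues: "The number and percentage of subjects experiencing adverse events for each body system and preferred term will be displayed by phase of study". It does not list the phases, say which date puts an AE in a phase, say what happens to an AE that runs across a phase boundary, or say whether the maximum is taken within a phase or over the whole study. The nearest thing to a rule is in SAP 12.1.3.2, where the follow-up table "contains a summary of only those adverse events which occurred within 4 weeks after the last dose of study medication".

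**Primary period.** Protocol 11.3 states: "The primary analysis will be conducted on data obtained during the 4-week PK period of the study". Protocol 6.2.2 plans a first report once all patients have finished 4 weeks and a further report after the 48-week extension.

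**The concern.** Severity and timing are both named in the primary objective and the primary endpoint (Protocol 3.1 and 3.3). A table of severity by phase combines the two, so it needs to know what grade an AE had reached in each phase. The recording rules keep only the worst grade over the whole episode and only the date on which the episode began.

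For an AE that is mild before Day 28 and severe months later, the data items listed in the protocol cannot show that the severe grade belongs to the extension. Two things are at stake. The 4-week column could carry severity that arose later. The extension, whose stated purpose is long-term safety, could fail to show a late worsening. The 4-week report and the final report could also disagree about the same 4 weeks, because the single grade would be raised between them.

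**Working it through.** The plan gives no figure on this point, so there is nothing to reproduce. The check traces one AE through the rules, and then sizes the effect.

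**1. Inputs**
- One grade per episode, the highest (Protocol 9.5).
- One onset date, one resolution date and no grade-change date (Protocol 9.3).
- Severity shown by phase (SAP 12.1.3.3).
- PK phase of 4 weeks (28 days), treatment to Day 364, follow-up visit on Day 392 (Protocol Table 2).
- Planned sample of 12 (Protocol 11.1).

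**2. Is there an assignment rule?** None is stated. SAP section 15 gives the uses of AE start dates as treatment emergence and the identification of unique occurrences; phase is not mentioned. The only worsening rule, in the definition of a treatment-emergent AE in SAP 12.1.1, concerns the first dose and not Day 28 or the end of treatment. Onset is still the likely choice: section 15 imputes missing start dates but leaves missing stop dates unfilled, and the AE listings are sorted by day of onset.

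**3. Trace of one hypothetical AE:** onset Day 10 at Grade 1, rising to Grade 3 on Day 150.

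| Rule applied | PK phase shows | Extension shows |
|---|---|---|
| Assign by onset, single maximum grade | Grade 3 | nothing |
| Count in every phase where ongoing, single maximum grade | Grade 3 | Grade 3 |
| Dated grades, maximum within phase | Grade 1 | Grade 3 |

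Both rules that can be applied with the listed items put Grade 3 in the PK phase. Only dated grades give the correct PK entry. Similarly, under assignment by onset, an AE that starts on treatment and worsens after the last dose would not enter the follow-up table.

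**4. When would a 4-week report be affected?** The report waits for the last boy to reach Day 28. A boy enrolled E days before him is then at study day 28 + E. The Day 150 worsening is in the database at that moment only if 28 + E ≥ 150, that is E ≥ 150 − 28 = 122 days. The documents do not give the length of enrolment. A report cut before the worsening would show Grade 1.

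**5. Window.** The PK phase is 28/364 = 7.7% of treatment days. After it there are up to 364 − 28 = 336 treatment days, or 392 − 28 = 364 days to the follow-up visit, in which the single recorded grade can rise. These are upper bounds.

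**6. Size at n = 12** (exact Clopper-Pearson limits)
- 0/12: upper limit 1 − 0.025^(1/12) = 26.5%, so 0% (0 to 26.5%).
- 1/12: lower limit 1 − 0.975^(1/12) = 0.2%. The upper limit solves (1 − p)^12 + 12p(1 − p)^11 = 0.025, giving 38.5%. So 8.3% (0.2 to 38.5%).

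Each affected boy therefore moves a PK-phase severity percentage by 1/12 = 8.3 points. The intervals are added here for scale; the SAP plans counts and percentages for AEs.

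**The case against.** The strongest reply is that nothing in the plan says AEs go to a phase by onset, so misplacement is not demonstrated. That stands. A reader might infer that the primary 4-week analysis will show late severe events as severe. The documents do not support that. Protocol 11.3 limits the primary analysis to data obtained in the 4 weeks, and a promptly cut report would carry the grade reached by then. What remains is that the listed items give no means of applying that limit once the grade has been raised.

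Other replies have partial force:
- **The list in Protocol 9.3 is not called exhaustive.** The eCRF and its completion guidelines are not public, and a site might enter a worsening as a new AE. True, but neither 9.3 nor 9.5 asks for it, so practice could differ between sites.
- **AEs are assessed at every visit (Protocol 8.2.14) and the data-capture system keeps an audit trail (Protocol 13.4).** Source notes may show the course. The SAP plans no use of either, and the date of an edit need not be the date of worsening.
- **Much worsening is visible elsewhere.** This stands for laboratory and ECG findings, which are shown by visit (Protocol 11.7.2; SAP 12.2 and 12.4). The gap is therefore mainly in clinical AEs.
- **A Grade 3 event is not lost.** This also stands: it appears in the AE listing and in the overall worst-grade summary.
- **Recording the worst grade is ordinary practice.** Agreed. The instruction in 9.5 is not itself an error; the problem comes from combining it with a by-phase table.

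**Conclusion.** The point holds in a conditional form. For a clinical AE that begins in the PK phase and worsens after Day 28, the Day 28 grade cannot be recovered from the items the protocol lists, and the SAP has no rule for placing the AE or its grade. If assignment is by onset, the final by-phase table can show the later grade in the PK phase and omit the worsening from the extension or follow-up. A 4-week report has the same problem only if it is cut after the worsening, which depends on how staggered enrolment was.

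One such boy would change PK-phase Grade 3 or higher from 0/12 to 1/12. The case is hypothetical, and the documents give no frequency for such events. The effect is on a descriptive display; no test, error rate or decision rule depends on it. It is still worth correcting, because severity and timing are parts of the primary endpoint and the change is cheap.

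**What to change.** 1. **Protocol 9.3 and 9.5, and the eCRF:** record the date of each increase in grade, or open a new linked record when the grade rises, and say which applies.
2. **SAP 12.1.3.3:** name the phases and state the rule that assigns an AE to a phase. Count each subject at the highest grade attained within that phase. Include in the extension or follow-up column an ongoing AE whose grade increases there, and align the follow-up table in SAP 12.1.3.2 with the same rule.
3. **At minimum, for the primary 4-week analysis:** freeze the grade of each AE as of Day 28. The AE assessment at Visit 3 is the natural point to capture it, and the frozen value should be used in both the 4-week and the final report.
4. **Leave unchanged:** the worst grade per episode for the overall summary (Table 14.3.1.1).

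The cost is one eCRF date field or linked record, a few sentences in the SAP and slightly more AE data entry at sites. The sample size and visit schedule are unaffected.

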9.6. Follow-Up of Unresolved Adverse Events

All AEs should be followed up by the Investigator until they are resolved, or the Investigator assesses them as chronic or stable. Follow-up of any SAE that is fatal or life-threatening should be provided within one additional calendar week. The Investigator should consider protocol guidelines and use his/her discretion in ordering additional tests as necessary to monitor the resolution of such events. In the event of additional investigations, the PTC Therapeutics Safety Department or designee should be informed via e-mail or fax. A patient withdrawn from the study because of an AE must be followed by the Investigator until clinical recovery is complete and laboratory results have returned to normal, or until progression has been stabilized. Follow-up may need to continue after the patient has discontinued from the study, and additional investigations may be requested by the medical monitoring team.

9.7. Adverse Event Reporting Period

The first day of AE reporting will coincide with the day the first dose of study drug is administered. The AE reporting period for this study ends with the 4-week post-treatment follow-up visit, except as described in [Section 9.3](#). In addition, SAEs occurring in a patient after the study period should be reported to the sponsor if the Investigator becomes aware of them.

9.8. Investigator Site Adverse Event Reporting Requirements

Classification of an event as serious or non-serious (see [Section 9.1.2](#)) determines the reporting procedures to be followed. Investigator site reporting requirements for AEs are summarized in [Table 5](#).

Table 5: Investigational Site Requirements for Reporting Adverse Events

Classification	Reporting Time	Reporting Action
Serious	Within 24 hours	E-mail, fax or telephone call to the PTC Therapeutics Safety Department/designee within 24 hours.
	Within 5 calendar days	Provide photocopies or document scan of relevant source documents ^a (eg, progress notes, nurses' notes, laboratory and diagnostic test results, discharge summaries) as requested by the PTC Therapeutics Safety Department/designee.
	Per CRF submission procedure	Record and submit information on appropriate CRFs (eg, Medical History and Concomitant Medications CRFs)
AESI	Within 24 hours	E-mail, fax or telephone call to the PTC Therapeutics Safety Department/designee within 24 hours.
	Within 5 calendar days	Provide photocopies of relevant source documents ^a (eg, progress notes, nurses' notes, laboratory and diagnostic test results, discharge summaries) as requested by the PTC Therapeutics Safety Department/designee.
	Per CRF submission procedure	Record and submit information on appropriate CRFs (eg, Medical History and Concomitant Medications CRFs)
Nonserious	Per CRF submission procedure	Record and submit information on appropriate CRFs (eg, Adverse Events, Medical History and Concomitant Medications CRFs)

^a Patient name, address, and other personal identifiers should be obscured.

Abbreviations: AESI = AEs of special interest, eCRF = electronic case report form, IRB/IEC = Institutional Review Board/Independent Ethics Committee, SAE = Serious Adverse Event

For SAEs, in addition to completing the AE eCRF, the SAE report form must also be completed. The SAE report form should be signed by the Investigator; however, if the Investigator is unable to sign at the time of the event or within 24 hours, the form should be signed by the clinical staff member reporting the SAE (eg, the study coordinator). The SAE report form must be faxed or emailed to the PTC Therapeutics Safety Department or designee and to the site IRB/IEC (if required by local regulations) within 24 hours. Follow-up information to the SAE should be clearly documented as “follow up” in the SAE report form and must also be faxed or emailed to the same parties. All follow up SAE report forms for the event must be signed by the Investigator. Any source documents (eg, progress notes, nurses' notes, laboratory and diagnostic test results, discharge summaries) provided to the sponsor must be redacted so that the patient's name, address, and other personal identifiers are obscured. Only the patient's study number and initials are to be provided (in regions where the provision of such information is permitted). The information in the AE eCRF and the SAE report form(s) must match or be reconciled. Where the same data are collected, the forms must be completed in a consistent manner. For example, the same AE term should be used on both forms.

In the rare event that the Investigator does not become aware of the occurrence of an SAE immediately (for example, if a patient initially seeks treatment elsewhere), the Investigator is to document his/her first awareness of the AE and report the event within 24 hours after learning of it.

The PTC Therapeutics Safety Department/designee contact information for reporting SAEs is provided below. This information is also provided in the Investigator File and the back-up paper SAE report form.

PTC Therapeutics Safety Department

Attention: [REDACTED]

Telephone: [REDACTED]

Facsimile: [REDACTED]

E-mail: [REDACTED]

9.9. PTC Therapeutics Adverse Event Reporting Requirements

As the sponsor of the study, PTC Therapeutics is responsible for reporting certain safety information, particularly SAEs and patient deaths related to participation in the study, to each Investigator in an expedited manner. If notification of an AE requiring expedited reporting to investigators is received, PTC Therapeutics or its designated representative will contact each investigational site participating in this study by e-mail, fax, and/or overnight mail such that the Investigator can promptly notify the site IRB/IEC per their local requirements. The initial expedited safety report will be provided as required according to local regulations (eg, within 15 days) after the earliest date PTC Therapeutics or an agent of PTC Therapeutics (eg, a site monitor) becomes aware of an AE. This awareness date is the date the regulatory reporting clock begins and the date is considered Day 0.

10. WITHDRAWAL OF SUBJECTS

All patients who receive ataluren should remain in the study whenever possible. However:

- The parent/caregiver has the right to withdraw consent and discontinue ataluren at any time.
- If the patient's condition substantially worsens after initiating ataluren, the patient will be carefully evaluated by the Investigator. The patient will be withdrawn from treatment if continuing would place them at risk.
- The Investigator may withdraw the patient from ataluren, if, in the Investigator's clinical judgment, it is not in the patient's best interest to continue.
- In the event that the patient becomes significantly noncompliant with ataluren administration, study procedures, or study requirements, the patient should be withdrawn from ataluren when the circumstances surrounding noncompliance increase risk to the patient or are anticipated to substantially compromise the interpretation of study results.
- This study may be discontinued by the relevant regulatory authority, IRB/EC, and/or PTC Therapeutics at any time.

The date ataluren is discontinued and the reason for discontinuation will be recorded in the source documents and in the eCRF. The PTC medical monitor (or designee) should be informed via e-mail of when a patient discontinues study drug.

When ataluren is discontinued (regardless of the reason), the Investigator is expected to capture all of the evaluations required at the end of treatment or Follow-up and any additional evaluations should be completed that may be necessary to ensure that the patient is free of untoward effects. The patient should be encouraged to seek appropriate follow-up for any continuing health problems.

11. STATISTICAL CONSIDERATIONS

11.1. Sample Size

The sample size of 12 patients for this study is not based on formal statistical considerations. However, preliminary results from population PK (popPK) simulation indicate that the current study design (sample size and sparse sampling strategy) will provide adequate precision for the prediction of PK parameters (apparent clearance and volume of distribution) even considering the usual potential for subject dropouts and/or missing samples [[Wang 2012, FDA General Clinical Pharmacology Considerations for Pediatric Studies for Drugs and Biological Products 2014](#)].

11.2. Analysis Populations

All patients who receive at least 1 dose of ataluren will be included in the analyses of safety. For each outcome measure, evaluable populations of patients will be considered to comprise all patients who have sufficient baseline and on-study measurements to provide interpretable results for the test of interest.

11.3. General Statistical Considerations

By-subject listings will be created for each eCRF module. Summary tables for continuous variables will contain the following statistics: N, mean, median, standard deviation, standard error, minimum, maximum, and 95% confidence intervals (CIs) as appropriate. Summary tables for categorical variables will include N and percentage. Graphical techniques will be used when such methods are appropriate and informative.

Transformations of the data may be explored if warranted by the distribution of the data.

All analyses will be performed using Statistical Analysis System (SAS® Version 9.0 or higher).

The primary analysis will be conducted on data obtained during the 4-week PK period of the study and may be reported separately from the extension study data.

